4.2 Rationale for Study

Before embarking on a full scale study of thrombolysis during *ex situ* perfusions of DCD livers, we wish to undertake a pilot study to check safety and efficacy.

4.3 Investigational treatment

Alteplase (Actilyse, Boehringer Ingelheim, Germany) is a tissue plasminogen activator used routinely for the treatment of thrombotic occlusive events. *In vivo* it relies on the presence of plasminogen in clots and in the circulation which it breaks down to form plasmin, which is the active lytic component. Alteplase has a very short half-life *in vivo* (5 minutes according to the Summary of Product Characteristics, SmPC ⁶).

In the *ex situ* circuit there is no plasminogen circulating, although the liver will make some as time progresses; instead a plasminogen source is required and is readily available in the form of fresh frozen plasma (FFP) which has previously been shown to be effective as a perfusate component in NESLiP ⁷ as well as being a good source of plasminogen ⁸.

4.4 Data from non-clinical studies

The use of plasmin to clear microthrombi in DCD organs was first reported in Japan where rat lungs perfused *ex situ* were treated to clear the pulmonary circulation⁹. This followed work showing how urokinase could be used to achieve a similar effect in a dog DCD lung transplant model¹⁰.

4.5 Data from clinical studies

Clinical studies of TPA relate to its use *in vivo* for cerebral and coronary thromboses, and for the treatment of pulmonary emboli. There are no reports of its use in an *ex situ* clinical setting.

4.6 Risks and benefits

The main risk of thrombolytic therapy is bleeding, but since this treatment will take place *ex situ*, and there will be a 60 minute washout period, there is likely to be little TPA left circulating. The plasma half-life of TPA *in vivo* is 4 to 5 minutes⁶. When the liver is removed from the perfusion machine it is flushed with 2 to 3 litres of preservation solution before being implanted, washing away any last traces of perfusate.

4.7 Dose / Regimen

There are a variety of infusion regimens in the SmPC dependent on body weight and on the disease being managed⁶.

The first regimen used in the research studies involved a 10mg bolus at the start of perfusion and an infusion of 40mg over 80 minutes (0.5mg/h) together with a 50ml bolus of FFP and an infusion of 200mls over 80 mins (2.5mls/h). Although this cleared the common duct of one liver had some fibrin plugs within it.

A subsequent regimen involved a 5mg bolus of TPA with 25mls of FFP, and an infusion of 45mg TPA and 225mls FFP over 3 hours.

Alternative regimens have been evaluated. The results suggest a 1 hour infusion is optimal, based on d-dimer release, with 50mls FFP loading at the outset followed by an infusion over an hour.

Following independent protocol review, this study will involve 3 initial treatment groups with total doses of 10, 20 or 50mg alteplase, with a 20% loading dose and 80% infusion given over 1 hour. There will be 6 transplanted livers in each of these groups, with at least one in each group receiving FFP and no alteplase. Following these groups D-dimer levels on perfusates over the first 2 hours will be run to determine the efficacy in fibrinolysis. Following that the smallest dose associated with optimal fibrinolysis will be chosen for the next two groups. The fourth group will comprise an infusion into the portal reservoir, rather than into the hepatic artery cannula to assess efficacy of this approach, and the fifth group will be over 2 hours instead of one, to assess whether this gives additional benefit in terms of D-dimer release.

Group A: 2mg alteplase bolus and 8mg infused over 1 hour

Group B: 4mg alteplase bolus and 16mg infused over 1 hour

~~Group C: 10mg alteplase bolus and 40mg infused over 1 hour~~ – cancelled in light of efficacy of 10mg dose

Group D: 10mg alteplase, infused over 1 hour into the portal reservoir

Group E: 10mg alteplase, infused over 2 hours either into the portal reservoir or hepatic artery cannula, depending on results of Group D.

Groups A, B, and D will all get 50mls FFP bolus and 200mls infused over 1 hour, and Group E will get FFP infused over 2 hours as a source of plasminogen.

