Maximum duration of treatment of a subject	The recipient is not treated, just the liver. Treatment of the liver lasts 60 minutes

2 General information

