2.9 Trial summary

Livers from donors donating after circulatory arrest (DCD donors) are associated with a high incidence of bile duct strictures after transplantation. This remains the case for liver subject to *ex situ* normothermic perfusion (NESLiP) prior to transplantation, with a rate of around 20% for anastomotic and non-anastomotic strictures. Livers from brain dead donors have a lower incidence of strictures after NESLiP at around is 8%, but they are equally disabling. Recent work in Cambridge has shown that DCD livers during NESLiP develop infarcts in the stromal walls of bile ducts in association with fibrin plugs in the peri-biliary blood supply, suggesting that these fibrin plugs may be the cause of the stromal infarcts, and by extrapolation the bile duct strictures. Subsequent work has shown that by using a similar thrombolytic protocol with tissue plasminogen activator (TPA, alteplase) to that used for clearing clots from the coronary circulation in patients having heart attacks results in no visible fibrin plugs and no bile duct necrosis.

In this study livers will undergo NESLiP and receive an infusion of TPA using a standard thrombolytic regimen for the first 60 minutes of perfusion, with a minimum perfusion time of 2 hours. Alteplase has a half-life of 5 minutes *in vivo* and a 1 hour perfusion will mean there will be at least 60 minutes between the end of the TPA infusion and removing the liver from the machine. Not all DCD donor livers will be viable on testing during NESLiP, but experience suggests that two thirds will meet the viability criteria and be transplanted. It is unlikely that there will be any active TPA in the circuit at the point of removal from the machine. Recipients will then undergo standard follow up with no further research intervention.

This study is a pilot study of 30 DCD and 30 DBD transplants to assess the safety of thrombolysis during *ex situ* perfusion, and to give an idea of its effects on the subsequent outcome of the implanted liver with particular reference to early function and bile duct strictures. The results will be compared with recipients randomised to receive FFP and no TPA. If the study suggests that the intervention is safe and efficacious the protocol will be used in a larger scale multicentre study.

3 Study Flow Chart

Donor liver placed on OrganOx *metra* machine

[figure not shown]

Figure 1: Flow chart for NESLiP assessment of donor livers

4 Background

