8.2 Trial material / source of drugs / presentation of drugs

Alteplase will be reconstituted with sterile water: 10mls for 10mg dose; 20mls for 20mg dose, and 50mls for the 50mg dose, to make a 1mg/ml solution. It should be drawn up into a 50ml syringe to which Normal saline will be added (10mg and 20mg doses only) to achieve a final volume of 50mls. The syringe containing alteplase will be placed on a syringe driver and connected to a three-way tap attached to the arterial cannula within the liver container for the first 3 groups, and on the portal reservoir for the 4th group. The site of infusion for the 5th group will be determined from a D-dimer analysis after completion of the first 4 groups.

One unit of fresh frozen plasma (approx. 250mls) will be run through a giving set or divided into five 50mls syringes; 50mls will be added to the soft shell reservoir, the remaining 200mls will be delivered over 60 mins using an infusion pump or syringe driver to the second port of the three-way tap.

Once the liver is placed on the circuit **and as perfusion is begun**, 20% of the total dose of alteplase for the study group (see below) is infused through the arterial cannula (groups A, B, and C) or portal reservoir (group D). The remainder of the dose delivered to the arterial cannula / portal reservoir infused over one hour.

Group	Alteplase bolus dose (mg)	Alteplase infusion dose (mg)	Infusion site
A	2	8	Hepatic artery cannula
B	4	16	Hepatic artery cannula
C	10	40	Hepatic artery cannula
D	2	8	Portal reservoir
E	10	0	To be decided

Addendum: The initial analysis of the 10mg dose data suggest this is more than adequate, so there will be no 50mg treatment arm (Group C).

It is important not to mix the FFP and alteplase before they are added by infusion since the plasminogen in FFP will be rapidly converted to plasmin, and this plasmin will itself be broken down rapidly afterwards.

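### Group E is dosed two ways (2-hour delivery in 4.7, all bolus in 8.2), and under 4.7 the 2-hour minimum perfusion no longer guarantees the 60-minute washout

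*Protocol*

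**What the plan says.** Protocol 4.7 defines the arm as "Group E: 10mg alteplase, infused over 2 hours". Its purpose is given there too: "the fifth group will be over 2 hours instead of one, to assess whether this gives additional benefit in terms of D-dimer release". The plasma follows the same timing: "Group E will get FFP infused over 2 hours as a source of plasminogen". No bolus/infusion split is given for this group's alteplase.

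Protocol 8.2, the section on preparing and giving the drug, differs. Its table has columns for bolus dose, infusion dose and site, and the Group E row reads "E 10 0 To be decided". The sentence on the 20% starting dose covers only the other groups: that dose "is infused through the arterial cannula (groups A, B, and C) or portal reservoir (group D". The remainder is then given over one hour. For the plasma, after the first 50 ml, "the remaining 200mls will be delivered over 60 mins using an infusion pump or syringe driver", with no exception for Group E.

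The synopsis entry for maximum treatment duration says "Treatment of the liver lasts 60 minutes".

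On perfusion time, 2.9 describes a 60-minute TPA (alteplase) infusion "with a minimum perfusion time of 2 hours" and infers a gap of at least 60 minutes before the liver leaves the machine. Section 4.6 then gives a 60-minute washout, without excepting any group, as one reason why little TPA should remain. The other reasons are ex situ delivery, the short half-life and a 2 to 3 litre flush.

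**The concern.** The same 10 mg is a 2-hour delivery in one section and entirely a bolus in another. The two readings lead to different harms, and only one can apply to a given liver.

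- **If 8.2 is followed**, Group E receives alteplase at once and its plasma over one hour. It then says nothing about whether 2-hour delivery releases more D-dimer. The washout is not lost.
- **If 4.7 is followed**, the infusion can end at the moment the minimum perfusion time is reached. A liver could be removed with no washout while still complying with the protocol.

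The second reading matters because excess bleeding is part of the primary objective (4.9.1), post-reperfusion blood loss is a primary endpoint (5.6.1), and residual thrombolytic activity after transplant is a reason to end the trial (5.8.3).

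**Working it through.** **Inputs from the protocol**
- Minimum perfusion: 120 min (2.9).
- TPA infusion time: 60 min for the one-hour groups; 120 min for Group E (4.7); none for Group E (8.2 table).
- Total alteplase: 10 mg for Groups A, D and E. Split: 20% bolus and 80% infusion for the initial groups (4.7).
- Half-life: 4 to 5 min in vivo (4.6). No ex situ value is given.
- FFP: 50 ml bolus plus 200 ml (4.7, 8.2).

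**Guaranteed washout** = minimum perfusion - infusion time
- One-hour groups: 120 - 60 = 60 min. This reproduces the figure in 2.9.
- Group E under 4.7: 120 - 120 = 0 min.
- Group E under 8.2 (bolus only): 120 - 0 = 120 min.
- Perfusion needed to keep 60 min under 4.7: 120 + 60 = 180 min.

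**FFP rate**: 200 ml over 1 h = 200 ml/h under 8.2; 200 ml over 2 h = 100 ml/h under 4.7.

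**Illustrative TPA in the circuit before the flush.** The model is one-compartment with first-order loss, k = ln 2 / half-life. For an infusion at rate r lasting T minutes, the amount at the end is (r/k)(1 - e^(-kT)), plus any bolus × e^(-kT). It then halves once per half-life.

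At a 5-minute half-life, k = 0.693/5 = 0.1386 per min:
- Group E under 4.7 at 120 min, no bolus: (10/120)/0.1386 = 0.601 mg.
- Group E under 4.7 at 120 min, 2 mg bolus plus 8 mg: (8/120)/0.1386 = 0.481 mg (the bolus remnant is negligible).
- One-hour regimen, 2 mg plus 8 mg: 0.962 mg at 60 min; × 2^(-12) = 0.000235 mg at 120 min.
- Group E at 180 min: 0.601 × 2^(-12) = 0.000147 mg, or 0.481 × 2^(-12) = 0.000117 mg.

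Because the ex situ half-life is not given, I assumed a range of 4 to 30 minutes:

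| Half-life (min) | One-hour 10 mg regimen at 120 min (mg) | Group E at 120 min, no bolus (mg) | Group E at 120 min, 20/80 split (mg) |
|---|---|---|---|
| 4 | 0.000023 | 0.481 | 0.385 |
| 5 | 0.000235 | 0.601 | 0.481 |
| 10 | 0.030 | 1.20 | 0.96 |
| 30 | 1.21 | 3.38 | 2.83 |

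At 30 minutes, a 180-minute minimum would leave 3.38 × 2^(-2) = 0.85 mg or 2.83 × 2^(-2) = 0.71 mg in Group E.

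**The case against.** Removal at exactly 120 minutes is unlikely. The criteria in 5.8.1.1 include glucose falling after 2 hours and bicarbonate need over the first 4 hours, which cannot be fully read at 120 minutes. The same section warns that assessment at 2 or 4 hours may be too early, and perfusate samples are scheduled at 180 and 240 minutes. This stands as a reason to expect longer perfusion, but none of it sets a minimum. Livers perfused for 3 hours or more keep the 60 minutes; only the guarantee is lost.

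Section 2.9 ties its 60-minute gap to a one-hour infusion and so makes no claim about a 2-hour one. That is fair, although 2.9 describes the one-hour infusion as what livers in this study receive. The statement in 4.6 has no such condition.

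The residual amounts depend on the half-life. At 30 minutes the contrast with the one-hour regimen falls from thousands-fold to under three-fold (3.38/1.21 = 2.8), and a 180-minute minimum would not clear the drug. All figures precede the flush, and the protocol links no amount to bleeding. This stands, so the amounts are illustrative. The loss of the 60 minutes does not depend on them.

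The intended regimen can largely be inferred: the table in Amendment 3 (2.7.3) gives Group E plasma at 100 ml/h, consistent with 4.7. That identifies 8.2 as the section to correct, but it does not correct it. D-dimer release is also a secondary endpoint, which limits the scientific loss under 8.2.

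**Conclusion.** The concern holds. The current text gives Group E two incompatible regimens, and 8.2, the section with the administration instructions, would defeat the arm's purpose. If 4.7 governs, the guaranteed washout is 0 minutes against the 60 stated in 4.6. This follows from the stated times alone, assuming the infusion begins with perfusion as 8.2 directs for the other groups. The amount of TPA present at 120 minutes, about 0.48 to 0.60 mg at a 5-minute half-life, rests on a one-compartment model and on applying an in vivo half-life to the circuit. Over the assumed 4 to 30 minutes it runs from 0.38 to 3.4 mg. The two harms are alternatives, but the document needs correction under either reading. That should happen before any Group E liver is treated.

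**What to change.** - Replace the 8.2 Group E row with the 2-hour regimen of 4.7, and state the split: 2 mg bolus plus 8 mg over 2 hours if the 20%/80% rule is to apply.
- Extend the 8.2 administration text to Group E, including its FFP rate: 100 ml/h if 200 ml is infused over 2 hours.
- Change the maximum treatment duration in the synopsis to match.
- In 2.9 and 4.6, require at least 60 minutes between end of TPA infusion and removal in every group, which means at least 180 minutes of perfusion for Group E. Record that interval for each liver.

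The cost is amendment wording and one data item. Group E livers that would otherwise come off between 120 and 180 minutes stay on for up to 60 minutes longer; those already perfused for 3 hours or more are unaffected.

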4.8 Population

Patients with liver disease awaiting transplantation who have agreed to receive a liver from a DCD or DBD donor.

4.9 Trial objective and purpose

4.9.1 Primary objective

To evaluate the safety and feasibility of thrombolytic therapy delivered *ex situ*, viz:

- Is it possible to safely treat livers on the perfusion machine with a clot busting regimen?
- Is it associated with excess bleeding in the recipients?

4.9.2 Secondary objectives

- To assess the effects of thrombolytic therapy on early liver function
- To evaluate the efficacy of delivering a thrombolytic treatment *ex situ* to clear fibrin/red cell plugs and prevent symptomatic biliary strictures and obtain data on efficacy to power a larger study

5 Trial Design

5.1 Statement of design

This is a three arm open label pilot study

5.2 Number of Centres

Three centres

5.3 Number of Subjects

Around 60 transplant patients will be recruited. However, since approximately a third of DCD livers undergoing NESLiP will not pass viability criteria, approximately 45 DCD livers will need to be perfused. Similarly, around 15% of DBD livers undergoing perfusion do not pass viability criteria so around 35 DBD livers will need to be perfused.

5.4 Sample size determination

Previous experience with back-to-base perfusion of DCD livers has been associated with a 20% incidence of anastomotic strictures and a 20% incidence of non-anastomotic bile duct strictures (unreported Cambridge data). In a cohort of 20 patients receiving a DCD liver treated by NESLiP it is likely that one will die, five will undergo retransplantation and four will develop non-anastomotic strictures. Similarly, the incidence of non-anastomotic strictures in DBD livers undergoing NESLiP in Cambridge is 8%, with a further 15% suffering anastomotic strictures.

A sample size of 30 DBD and 30 DCD should allow us to evaluate the safety of this therapy. It may also help determine whether the thrombolytic regimen increases the proportion of perfused livers that get transplanted and abolishes non-anastomotic strictures, and therefore whether it is worth proceeding to a formal randomised study and how to power that study

5.5 Study duration

The study will continue until all the subjects are recruited. In a normal year, Cambridge perfuse 25 DCD livers and 25 DBD livers and the Royal Free a similar number. Recruitment should thus be complete within a year and possibly sooner, allowing for patients declining consent and livers not being viable.

5.6 Study endpoints

5.6.1 *Primary endpoint*

- Post reperfusion intra-operative blood loss
- Feasibility of adding TPA and FFP to livers undergoing normothermic perfusion before transplantation

5.6.2 *Secondary endpoint*

- Return to theatre in first 24 hours for bleeding
- Total and post reperfusion intra-operative blood transfusion
- Liver utilisation: proportion of liver perfusions resulting in a transplant
- Incidence of symptomatic anastomotic and non-anastomotic strictures at 6 months post-transplant
- Incidence of any anastomotic or non-anastomotic stricture excluding those related to hepatic artery thrombosis
- Incidence of “clinically relevant” non-anastomotic strictures, using the van Rijn definition¹¹
- Incidence of post reperfusion syndrome: 30% fall in mean BP lasting at least a minute in the first 5 minutes post reperfusion or the need for adrenaline or doubling of noradrenaline to support the circulation.
- Early allograft function (Olthoff criteria¹² and MEAF score¹³)
- Incidence of hepatic artery thrombosis in the first 6 months
- Incidence of acute kidney injury (RIFLE criteria)
- D-dimer release into perfusate compared to controls

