5.8 Criteria for Discontinuation

5.8.1 *Individual liver*

5.8.1.1 *Transplant criteria*

Criteria favouring transplantation of liver include:

Perfusate:

- ALT < 6000 u/L

- Lactate fall to <2 in 2 hours
- Glucose falling hour on hour after 2 hours
- Producing bile
- Need for <40mls 8.4% NaHCO₃ in the first 4 hours to maintain a perfusate pH>7.2 as measured on near patient blood gas machine (not the Organox *metra* reading)

Bile

- pH>7.6
- Bile glucose <2.0mmol/L or >10mmol/L less than perfusate.

Criteria favouring non-use of liver include

Perfusate

- ALT>10000iu/L
- Lactate>2.5 at 2 hours
- Glucose failing to fall after the second hour
- Not producing bile
- Requirement for >60mls 8.4% NaHCO₃ in first 4 hours of perfusion

Bile

- pH<7.5
- Bile glucose >2.0mmol/L or <10mmol/L less than perfusate

The above criteria reveal an area of uncertainty with livers between the definitely usable and definitely unusable. There are currently no internationally accepted viability criteria, but those proposed by ourselves are in accord with most other criteria, and are based on the largest published experience to date^{14,15}. That said, a recent case, and the reason for amendment 5, has suggested that assessment at 2 or 4 hours may be too soon and a longer period of perfusion may be advisable in some livers to distinguish between a liver that will not recover, and one that is stunned and recovers after 4 hours.

5.8.1.2 *Livers outside criteria with late recovery of function*

Where the criteria are outside those favouring transplantation, but the liver appears to recover function as perfusion continues, a decision to use the liver will be taken in consultation with a member of the transplant team who is not involved in the research (typically both the on call hepatologist and surgeon), and the appropriateness of the proposed recipient will also be reviewed. It may be necessary to change recipient if there remains doubt over the liver

5.8.1.3 *Change of recipient after liver treatment has begun*

Any decision to change recipient will need to go through the national liver offering protocol, that is, it will need to be offered back to all other centres as a “Fast Track” offer and only if they decline its use can it be reallocated locally (unless it was originally accepted as a Fast Track with no named recipient when there is no need to offer the liver back).

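### The bleeding comparison ignores the time from end of TPA to removal of the liver, so a null pooled result would not by itself support the 2-hour minimum perfusion

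*Protocol*

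**What the plan says.** Protocol 2.9 describes a 60-minute TPA infusion "with a minimum perfusion time of 2 hours" and concludes that "there will be at least 60 minutes between the end of the TPA infusion and removing the liver from the machine". Section 4.6 builds the bleeding argument on this: "there will be a 60 minute washout period, there is likely to be little TPA left circulating". Two further supports are given. One is pharmacokinetic: "Alteplase has a half-life of 5 minutes" in vivo (2.9; 4 to 5 minutes in 4.6). The other is mechanical: after removal "it is flushed with 2 to 3 litres of preservation solution before being implanted" (4.6). No ex situ half-life is stated, and section 4.5 reports no previous clinical use ex situ.

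No maximum perfusion time is stated. The viability criteria in 5.8.1.1 use lactate at 2 hours and bicarbonate need over 4 hours, and the text adds that "assessment at 2 or 4 hours may be too soon and a longer period of perfusion may be advisable in some livers".

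The primary safety endpoint is "Post reperfusion intra-operative blood loss" (5.6.1). Section 10.3 compares TPA livers with control perfusions. Section 10.5 names the Kruskal-Wallis and Fisher tests. Section 10.6 matches historical DCD comparators on agonal phase, cold ischaemia and donor liver index. Sections 9.4 and 9.5 list the data to be recorded. None of these mentions the interval after TPA or the duration of perfusion.

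The stated consequence is in 2.9: "If the study suggests that the intervention is safe and efficacious the protocol will be used in a larger scale multicentre study".

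**The concern.** If TPA given ex situ makes a recipient bleed, the likely route is activity still present when the liver leaves the machine. The time since the end of the infusion is therefore the exposure that matters, and the protocol's own safety reasoning is expressed in it. It will differ between recipients for reasons unrelated to the trial.

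A comparison of all TPA recipients with controls averages over that exposure. If many livers stay on the machine well beyond 2 hours, a reassuring result describes mainly those livers. The shortest permitted interval, which is the one that needs testing, would pass into the larger study with little evidence of its own.

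**Working it through.** **1. The protocol's own interval.** Minimum interval = minimum perfusion time − infusion time (2.9, 4.7).

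| Removal at | 1-hour infusion (A, B, D) | 2-hour infusion (E) |
|---|---|---|
| 2 h | 120 − 60 = 60 min | 120 − 120 = 0 min |
| 4 h | 240 − 60 = 180 min | 240 − 120 = 120 min |
| 6 h | 360 − 60 = 300 min | 360 − 120 = 240 min |

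The stated 60 minutes is reproduced for the 1-hour groups but not for Group E. The 4 h and 6 h rows are illustrations, because the protocol gives no distribution of perfusion times.

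**2. TPA left in the circuit before the flush.** Fraction = 0.5^(interval / half-life). Only the 5-minute half-life is in the protocol. The others are assumed ex situ values.

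| Half-life | 60 min | 120 min | 180 min |
|---|---|---|---|
| 5 min (in vivo) | 0.024% | about 0 | about 0 |
| 15 min (assumed) | 6% | 0.4% | 0.02% |
| 30 min (assumed) | 25% | 6% | 1.6% |
| 60 min (assumed) | 50% | 25% | 12.5% |

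On the protocol's premise, 60 minutes is 12 half-lives and no excess is expected. The interval matters only if clearance ex situ is slower, which this pilot would be the first to examine in patients.

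**3. Dilution.** One transplanted liver in six receives FFP only (section 7), so 60 / 6 = 10 controls and 50 TPA recipients. Suppose an excess of d = 1 SD (assumed) occurs only in a fraction f of TPA recipients.

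- Pooled difference = f × d.
- Variance in the TPA group = 1 + f(1 − f)d².
- Standard error = √[(1 + f(1 − f)d²)/50 + 1/10].
- Power to show an excess (two-sided 0.05, normal approximation) = Φ(f × d / SE − 1.96).

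For f = 20%: SE = √(1.16/50 + 0.1) = 0.351, and Φ(0.2/0.351 − 1.96) = Φ(−1.39) = 0.08.

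| f | Pooled difference (SD) | Pooled power |
|---|---|---|
| 10% | 0.1 | 0.05 |
| 20% | 0.2 | 0.08 |
| 30% | 0.3 | 0.13 |
| 50% | 0.5 | 0.29 |
| 100% | 1.0 | 0.82 |

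**4. What looking by interval can deliver.** Power for the same 1 SD excess in short-interval recipients alone is Φ(1/√(1/n + 1/m) − 1.96), with n short-interval TPA recipients and m controls. The last column is the one-sided 95% upper bound after no events, 1 − 0.05^(1/n).

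| n | All 10 controls | Controls with similar perfusion (m = n/5) | Bound after 0 events |
|---|---|---|---|
| 5 | 0.45 | 0.15 (m = 1) | 45% |
| 10 | 0.61 | 0.25 (m = 2) | 26% |
| 15 | 0.69 | 0.35 (m = 3) | 18% |
| 25 | 0.76 | 0.53 (m = 5) | 11% |

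A regression of log blood loss on interval within TPA recipients was also simulated. Assumptions: blood loss doubled in short-interval recipients only; intervals of 1 to 1.5 h against 3 to 8 h; log-SD 0.7 to 0.9. Power was about 20% to 56% when 10% to 20% had short intervals. It fell to about 5% to 6%, no better than chance, if blood loss also rose about 10% per extra hour because weaker livers are perfused for longer.

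**The case against.** Five objections carry weight.

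- **No excess is expected.** With a 5-minute half-life and a flush of 2 to 3 litres, almost nothing should reach the recipient. This stands as the protocol's premise, and the residual fractions above are before the flush. But the half-life is an in vivo figure, and the pilot exists to test the premise.
- **Dilution depends on unknown perfusion times.** This stands. A reader might infer from the 4-hour criteria and sampling to 240 minutes that most livers will have 3 hours or more after TPA, so that harm would certainly be masked. The documents do not support that: lactate is judged at 2 hours, longer perfusion is foreseen only for some livers, and a sampling schedule is not a perfusion time. If most livers leave near 2 hours, dilution is small.
- **The analysis may be specified elsewhere.** An analysis by interval could be in an SAP, and the opening of section 10.4 could not be checked. Kruskal-Wallis also allows several groups. The recording lists in 9.4 and 9.5 are not exhaustive, since they omit blood loss too. So pooling is partly inferred from silence. Still, the endpoint, tests, matching factors and data items are fixed here, and none uses the interval.
- **Other safeguards exist.** Section 5.8.3 ends the trial on evidence of residual thrombolytic activity, section 9.5.1 samples perfusate and recipient blood just before removal, and section 10.7 has the sites review cases. These reduce the concern. The stopping criterion has no threshold, however, and none of them links bleeding to the interval.
- **The interval is not randomised.** Doubtful livers may be perfused for longer, and 5.8.3 notes that coagulopathy is common after DCD implantation. A regression could hide harm at short intervals. This stands, and it limits the remedy to description.

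**Conclusion.** The concern holds in a limited form. The protocol rests bleeding safety on a minimum interval, lets the interval vary upwards without a limit, and fixes its bleeding comparisons without using it. A pooled null result would therefore not by itself support the 2-hour minimum. Under an assumed 1 SD excess confined to short intervals, pooled power is 0.05 to 0.29 when 10% to 50% of TPA recipients are affected, against 0.82 when all are. The effect size, the shares and any ex situ half-life are assumptions.

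Two stronger readings are tempting. One is that excess bleeding would be missed; the documents show only that it could be. The other is that an analysis by interval would reliably detect it; with perhaps 5 to 15 short-interval livers and 1 to 3 comparable controls, it would not. What the extra analysis can do is show which intervals the safety conclusion covers.

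Separately, Group E's 2-hour infusion (4.7) and the 2-hour minimum with at least 60 minutes to removal (2.9) contradict each other as written.

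**What to change.** 1. In 9.5, list three times for every liver: end of TPA infusion, removal from the machine, and reperfusion. For FFP-only livers, record perfusion duration.
2. In 10.5 or 10.6, pre-specify a descriptive table of post-reperfusion blood loss, transfusion and return to theatre among TPA recipients, by band of the interval from end of TPA to removal. Show time to reperfusion as well. Place FFP-only recipients with similar perfusion duration beside each band, and give numbers and confidence bounds. State that the interval is not randomised and that longer perfusion may track poorer livers, so no causal test is claimed.
3. State that any safety conclusion covers only intervals observed in adequate number, and does not extend automatically to the 2-hour minimum.
4. Reconcile 2.9 and 4.6 with the Group E infusion in 4.7. The Group E row of the table in 8.2 (10 mg bolus, 0 mg infusion) also differs from 4.7 and leaves the end of TPA undefined for that group. Which passage is right is for the investigators to settle.

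The cost is three times that should already exist in machine and theatre records, plus one table. No extra patients, samples or procedures are needed. The bounds in the short-interval band will be wide, and the safety statement may be narrower than hoped.
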